The additional survey will assess participants' knowledge about electronic cigarettes, perception of electronic cigarette benefits and risks, willingness to use electronic cigarettes as a substitute for combustible cigarettes and will ask about their willingness to be contacted for future research about switching from cigarettes to electronic cigarettes.

Participants who agree to complete the survey will be provided with the options to complete the survey over the phone with a study team member or to have the survey emailed or texted out to them after a study team member has received their consent. Participants who are eligible for and complete the additional survey will receive a \$30 gift card.

We will aim to have 400 participants complete this survey.

Verification of smoking cessation: Due to COVID-19 and after discussion with the NCI Project officer, we will no longer be sending biochemical verification to patients. Patients who self-report 7-day abstinence at 3 and 6 months follow up will be considered non-smokers. Those who are enrolled prior to his change will continue to be sent biochemical verification and offered a \$20 incentive for each sample.

Biochemical verification of smoking cessation: Patients who self-report 7-day abstinence at 3 and 6 months follow-up will be asked to provide a saliva sample to assay for cotinine. Individuals will be offered a \$20 incentive for each sample.

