Biochemical verification process: **(This process ceased in March of 2020 due to the COVID pandemic)** The study RA will send to patients who report 7-day cigarette abstinence at 3 and 6 months follow-up a saliva cotinine collection kit and pre-paid packaging for return to the J2 laboratory (J2 Laboratories is a premier forensic drug and alcohol testing and clinical diagnostic laboratory located in Tuscon, AZ that has successfully partnered with the study team for previous saliva cotinine testing). The saliva sample will be tested for cotinine, which is a chemical the body makes from nicotine. The test will determine the study participant's exposure to cigarette smoke and nothing else. The cotinine and expired CO samples collected for the purposes of this study will not be stored for future uses not described in the protocol. Saliva samples will be destroyed after they are assayed for cotinine. After each results transfer, participants' data will be purged from the test company's files. The saliva cotinine collection kit will be marked only with the patient's unique study identification code, and will include: 1) instructions for successfully completing a sample; 2) an information sheet detailing the time and

date of the collection, 3) a brief survey reporting recent patient smoking history. The pre-paid packaging will include a FedEx package and pre-paid airbill for the subject to return their saliva sample directly to the lab. The lab will provide MGH directly with pre-paid airbills to be provided to participants. The return address on the airbill includes only the location of the research offices at MGH; no identifiable patient data will be provided to the lab. The J2 lab will send MGH a notice immediately upon receipt of a sample, and again upon testing with the results of the sample. Notices from the lab will be shared with MGH via email or a secure fax machine, and all attachments (invoices, testing results) include no identifiable information and are password protected.

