Patients who return a sample that is designated insufficient for testing by the lab will be offered the opportunity to complete additional samples. Patients who report use of NRT or e-cigarettes within the last week will be offered the opportunity to instead complete an expired air CO sample. The study RA will be trained in safe and proper use of the CO monitor and test results interpretation. As CO samples must be completed in-person, and with the aim of decreasing patient burden, samples will be completed at an existing clinic visit in accordance with patient preferences. We have successfully used these methods in previous work, with excellent return results (88%).^{58,60, 61}

Exit interviews: A sample of 72 patients (approximately 10% of anticipated 6-month survey completers) will be asked to participate in an in-depth individual interview, with one of the study staff, after completing the final survey. Sampling selection will be stratified by intervention group (approximately 9 per group). A semi-structured interview guide will be developed for telephone interviews. All patients will be asked about 1) smoking and quitting behaviors, 2) the enrollment process (e.g., timing, video recruitment messages, iPad use), 3) coordination with the LCS process, 4) understanding of their test results, and 5) adherence to LCS recommendation. Patients will be also asked for feedback on the intervention components (counseling content and duration, medication dose and access, and the community resources referral process) and about their overall satisfaction with the tobacco cessation counseling received. The sample size was determined to allow for 9 patients in each strata; analyses will compare results by strata. Interviews will last about 60 minutes, and patients will be provided \$20 remuneration.

Interviews will be audio-recorded, transcribed and analyzed. To ensure coding reliability, discrepancies will be resolved through discussion and comparison to raw data. Coding will continue until a high level of reliability (Kappa = ≥ 0.80) is established. Utilizing the mixed methods convergent design approach, qualitative data will be compared and contrasted to baseline and follow-up survey data.

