Organizational Readiness. Site characteristics and site readiness will be measured at each study site. Employees will undergo local training and then each attending employee will answer the readiness items, identified by the SCALE collaboration. Data will be collected anonymously, and employees will be consented through a waiver of documented informed consent. Responses to these items will be collected at baseline and at the end of the intervention phase of the study.

Research staff may also use a Partners approved text messaging service to contact patients who have agreed to be sent text messages during the consent process. This will be used to maximize outcomes from study videos, follow up surveys, and study reminders.

The Area Deprivation Index (ADI) is a measure for social economical status. We plan on using ADI to control for social and economical factors that are not otherwise reported. We plan on using census.gov to import a csv file of participant addresses which will return the 2020 census block group for those addresses. Names and study details will not be included in the process. By knowing the census block group of an address, we can then link that address to the 2020 ADI score.

VI. BIOSTATISTICAL ANALYSIS

Assessment Plan

Outcomes

Primary smoking outcome: 7-day point-prevalence tobacco abstinence at 6-month follow-up.

Secondary smoking outcomes (1) self-reported 7-day abstinence at 3-, and 6- months follow-up; (2) significant reduction (>50% decrease from baseline in cigarettes/day⁸¹); and (3) >24-hour intentional quit attempt at 3-, and 6-months follow-up.

Measures

Moderators

Sociodemographic and biological characteristics [baseline only]. *EHR*: Sex, age, primary insurance, language preference for sessions and study materials. *Survey*: Race/ethnicity, education level, employment, and religiosity. Medical history [baseline and follow-up]. *EHR*: Comorbid tobacco-related disease, ambulatory visits, alcohol consumption. Screening result. *EHR*: Lung RADS score, results of any diagnostic tests (CT or biopsy). Smoking characteristics [baseline and follow-up]. *Survey*: Current cigarettes/day, number of years smoked, e-cigarette use, past and current use of cessation medication and other tobacco products, 24-hour intentional quit attempt, nicotine dependence (2-item Heaviness of Smoking Index from the Fagerström Test for Nicotine Dependence [FTND] which have predictive validity with the overall FTND^{82, 83}).

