Proximal Outcomes/Mediators

All proximal outcomes/mediators will be assessed via survey at baseline and follow-up. Smoking beliefs. Readiness to quit (1 item 10-point 'contemplation ladder' ^{84,85}), importance and confidence to quit (1 item 10-point scales), 4 item perceived lung cancer risk, and 2 item perceived benefits of quitting.^{47,57} Health and screening beliefs. Self-reported overall health status (1 item from the SF-36 survey⁸⁶), 2 item perceived benefits of screening.^{47,57} Emotional symptoms. Anxiety and depression symptoms (PROMIS Anxiety and Depression 4a short-forms), worry about lung cancer (1 item about level^{87, 88}). Environmental factors. Living with a smoker in the household, 1 item 4-point scale about rules about smoking in the household⁸⁹, environmental workplace/hobby exposure and social support (PROMIS emotional and informational 4a short forms).⁸⁸

Analysis plan

All analyses will be intent-to-treat; we will classify patients who are lost to follow-up and those who do not provide a sample as current smokers.⁹² We will explore whether the mechanism of missing data is missing at random by comparing patient characteristics between those who complete follow-up vs. those who do not. We will perform sensitivity analysis: 1) limited to those who have complete data, and 2) multiple imputation for missing data.⁹³

Factorial design

In a factorial research design, two or more independent variables are concurrently examined within the same trial.^{94, 95} The three proposed factors will be crossed with one another to create a total of eight experimental conditions. An equal number of subjects will be randomly assigned to each condition, using a random number generator. This is not an 8-arm randomized controlled trial, but instead allows for an efficient examination of main effects for each variable over the entire sample of 640 subjects. This approach allows examination of three key treatment development questions in a much more time-efficient and economical manner by simultaneously performing three studies within the single trial. This achieves power to detect between-group differences that is equivalent to performing three separate randomized trials.⁹⁴

Outcomes/analysis

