Outcome measures will be assessed at baseline, 3-, and 6-months follow-up. At the outset, we will examine the frequency distributions of all variables. Data from all PHS sites will be pooled for analysis, after confirming there is no significant heterogeneity among sites or adjusting as needed. We will compare the baseline characteristics to assess whether randomization distributed covariates evenly. We will determine whether there is differential dropout in the groups and consider developing probability-of-completion weights to obtain unbiased estimates of treatment effect. The primary analysis will assess the effects of each intervention component in terms of its association with the **primary outcome** (cotinine-confirmed or self report of cessation at 6-months follow-up), **secondary smoking outcomes** and **proximal outcomes/mediators**: (a) short vs long counseling (conditions 1/2/5/6 vs. 3/4/7/8), (b) short vs long NRT (conditions 1/3/5/7 vs conditions 2/4/6/8), and (c) provision of systematic referral or not (conditions 1-4 vs. 5-8). Given the balanced complete factorial design,⁹⁴ each of the three main effect estimates will be based on the full sample size of 640. Cross-sectional analyses will be conducted for outcomes assessed at 3, and 6 months separately. For binary outcomes, chi-square tests will be used to compare the outcomes between groups for each follow-up time. For continuous outcomes two-sample t-tests or Wilcoxon rank sum tests, whichever more appropriate, will be used to compare between groups. A longitudinal analysis using Generalized Estimating Equations (GEE) techniques will also assess the overall impact of each component by including data from all follow-up time points. The secondary analysis will examine the interaction between components, which will provide insight into whether certain combinations of components are most useful. We will test the three-way and two-way interaction terms in the regression models. If there are component interactions, we will determine whether the components are synergistic or antagonistic. Exploratory analyses will examine the moderator effects on treatment effectiveness of the intervention components and groups. Of primary interest are sociodemographic characteristics (sex, race/SES, age), smoking characteristics (quit motivation, nicotine dependence), medical history, LCS-related factors (test results, and point of study entry), delivery modality selected (phone vs. video) and language of participation (English vs. Spanish). We will test the effects of these factors in multivariable logistic regression models to determine their association with the primary and secondary smoking outcomes. We will test for interactions between intervention and these factors to determine whether

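### The rule coding patients without a sample as smokers is not limited to those asked for one, so a self-reported quitter never sent a kit is coded two ways on the primary outcome

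*Combined protocol and SAP*

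**What the plan says.** Five places bear on how a patient is coded at 6 months.

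- **VI, Analysis plan.** After declaring that all analyses follow intention to treat, the plan states: "we will classify patients who are lost to follow-up and those who do not provide a sample as current smokers". Nothing restricts the second group to patients from whom a sample was requested.
- **V, Verification of smoking cessation.** Because of COVID-19, "we will no longer be sending biochemical verification to patients". It continues: "Patients who self-report 7-day abstinence at 3 and 6 months follow up will be considered non-smokers". It then makes an exception: "Those who are enrolled prior to his change will continue to be sent biochemical verification".
- **V, Biochemical verification process.** A note on the whole procedure reads: "This process ceased in March of 2020 due to the COVID pandemic". It makes no exception for patients already enrolled. The same part says that recent users of NRT or e-cigarettes "will be offered the opportunity to instead complete an expired air CO sample".
- **VI, Outcomes.** The primary outcome is "7-day point-prevalence tobacco abstinence at 6-month follow-up", with no mention of verification. Self-reported 7-day abstinence at 3 and 6 months is listed separately as a secondary outcome.
- **VI, Outcomes/analysis.** The primary outcome is restated as "cotinine-confirmed or self report of cessation at 6-months follow-up".

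All of this is current text. The Factorial design paragraph that follows the no-sample clause already carries the reduced sample size of 640.

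**The concern.** The coding of the primary outcome should not depend on which paragraph the analyst follows. Here it does for a whole class of patients: those reached at 6 months who report abstinence and were never sent a kit. Such patients cannot provide a sample, so the no-sample clause taken at its word makes every one of them a smoker.

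The primary outcome feeds the three main-effect tests. Under the Cost heading it also supplies the denominator of the incremental cost per quit. Because the clause sits under a statement about all analyses, it literally reaches the self-reported secondary outcome as well, which needs no sample by definition.

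**Working it through.** **Step 1. Code each type of patient under each rule.**

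| Patient at 6 months | Analysis plan | Verification paragraph (V) | Outcomes/analysis |
|---|---|---|---|
| Reports abstinence, never sent a kit | Smoker (no sample) | Non-smoker | Quitter, by self-report |
| Reports abstinence, asked, returns nothing | Smoker (no sample) | Non-smoker if read literally | Quitter if self-report alone suffices |
| Reports abstinence, asked, result does not confirm | No rule | Non-smoker if read literally | Not confirmed, but self-report alternative still open |
| No 6-month contact | Smoker | Not addressed | Not addressed |

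The first row is the contradiction. In the second row the Analysis plan does give a rule, but the self-report alternative in Outcomes/analysis could be read to override it. In the third row no explicit rule exists. Outcomes/analysis names only cotinine, so the status of the expired-CO alternative is also unstated.

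**Step 2. Who was asked?** Take a patient enrolled before the change who reached 6 months after March 2020. Under the Verification paragraph this patient is still sent a kit; under the process paragraph the procedure had ended. A clause limited to patients asked cannot be applied until these two agree.

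**Step 3. Reproduce the plan's power.** Inputs from Reduction from initial power calculations: effective N 768, so 384 per level; 10% vs 16% and 10% vs 17%. The Type 1 error rate is 0.05; two-sided is my assumption. With d = p2 − p1 and p̄ the mean rate:

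SE0 = √[2p̄(1−p̄)/n], SE1 = √{[p1(1−p1) + p2(1−p2)]/n}, power = Φ[(d − 1.96·SE0)/SE1].

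- 10% vs 16%: (0.06 − 1.96 × 0.02427)/0.02417 = 0.514, power 0.696 (plan: 70%).
- 10% vs 17%: (0.07 − 1.96 × 0.02466)/0.02453 = 0.883, power 0.811 (plan: 81%).

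The plan's figures reproduce from its stated effective N.

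**Step 4. Single 6-month comparison.** The chi-square test at 6 months uses 640/2 = 320 per level. For 10% vs 17%: (0.07 − 1.96 × 0.02702)/0.02687 = 0.634, power 0.737. This takes the rates as applying to all randomised patients. Expected quitters: 320 × 0.10 + 320 × 0.17 = 86.4.

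**Step 5. Apply the clause literally.** Let f be the share of self-reported quitters never sent a kit. The documents do not give f, so 30%, 50% and 70% are assumptions. Assume that f is equal at both levels of a factor and that every kit sent is returned and confirms. Both rates are then multiplied by (1 − f).

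| f | Rates | Difference (points) | Quitters counted | Risk ratio | Power |
|---|---|---|---|---|---|
| 0 | 10.0% vs 17.0% | 7.0 | 86.4 | 1.7 | 0.74 |
| 0.3 | 7.0% vs 11.9% | 4.9 | 60.5 | 1.7 | 0.56 |
| 0.5 | 5.0% vs 8.5% | 3.5 | 43.2 | 1.7 | 0.42 |
| 0.7 | 3.0% vs 5.1% | 2.1 | 25.9 | 1.7 | 0.27 |

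The risk ratio is untouched, but the absolute difference and the power fall. The cost-per-quit denominator, a difference in rates, shrinks by the same factor (1 − f).

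**The case against.** The best reply is that the contradiction needs an over-literal reading. The part of section V that describes biochemical verification says self-reported abstainers are asked for a sample, so the natural meaning of the clause is patients who were asked and did not respond. Section V gives an explicit rule for the period without kits, and a specific rule ordinarily governs a general missing-data sentence. An analyst who reads the whole document is unlikely to code every later self-reported quitter as a smoker.

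Much of this stands. The intent for patients never sent a kit can be recovered, which lowers the severity. It does not remove the contradiction: no passage limits the clause or says which rule governs, and recovering the intent does not settle who was asked or how a non-confirming result counts. The Outcomes list does not settle it either. It states the primary outcome without verification, but lists self-reported abstinence separately, which suggests that the primary outcome was not meant to be purely self-reported.

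It is also fair to say that the plan already has a rule for patients who were asked and returned nothing, and that nothing suggests a rule differing by arm.

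A reader might infer more than the documents support:

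- *That the trial will lose the power shown in the table.* Those figures belong to the literal reading, which is probably not intended, and to assumed values of f.
- *That f can be worked out from recruitment dates and the planned enrolment rate.* That gives a share of enrollees, whereas only self-reported abstainers are sent kits.
- *That power lost through unreturned samples measures this defect.* That loss remains after the wording is corrected.
- *That the clause is a known leftover from before the change.* This is plausible, but no version history is given.

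**Conclusion.** The point holds as an inconsistency in the written coding rule for the primary outcome. As written, the Analysis plan makes a self-reported quitter who was never sent a kit a smoker, while section V and Outcomes/analysis make the same patient a quitter. The latter two show the probable intent. Separately, section V conflicts with itself on whether patients enrolled before the change were still sent kits after March 2020.

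The size cannot be fixed from the documents, because the share of quitters never sent a kit is not reported. The illustrative range, from about 0.74 down to 0.56, 0.42 or 0.27, rests on shares of 30%, 50% and 70% that are equal across arms, full return of kits that were sent, a two-sided 0.05 test and 10% vs 17% among all 320 per level. It shows what the literal rule would do, not what the trial is expected to do. This should be fixed; it calls for a clarifying edit and not a redesign.

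**What to change.** Amend the Analysis plan and the related text as follows:

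1. Limit the no-sample clause to patients actually asked for a sample. Classify all others by their 6-month self-report, and as smokers if there is none.
2. Reconcile the two statements in section V on who was still sent verification after March 2020.
3. Keep the existing rule that patients asked who return nothing are smokers, and make clear that the self-report alternative in Outcomes/analysis does not override it.
4. State how a cotinine or expired-CO result that does not confirm abstinence is coded.
5. Apply the clause to the primary outcome and not to the self-reported secondary outcome.
6. Date the edit relative to interim analyses. Section IX provides for interim analyses throughout the trial and for any effectiveness results to go into the annual report. It does not say whether outcomes have been compared by arm. If they have, label the edit as made afterwards.

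The cost is about a paragraph of text and no new data. The downside is a primary outcome that is partly verified and partly self-reported, depending on the period, which section V already accepts.

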Smokers undergoing LCS are heavy smokers who likely need more intensive support. Initiating smoking early in life, heavy smoking, and having strong nicotine dependence are factors associated with less success in quitting, and these are common characteristics of smokers eligible for LCS. Over 40% of smokers undergoing LCS are heavy smokers ($>20/\text{day}$).³⁶ In our Project Reach, patients were older heavy smokers (mean age = 62, 41% smoking $>1\text{ppd}$) who had been smoking for an average of 46 years. Older smokers need more intensive interventions, but it is not clear what types of interventions would be most appealing and motivating for them.⁴⁸ Long-term heavy smokers also have social barriers to quitting (e.g., food insecurity) that may not be otherwise addressed.⁴⁹ Our work with low income older smokers suggests that addressing social barriers is key; use of systematic referral, a community resource and referral database, was significantly associated with quitting.⁵⁰ Reflecting the chronic nature of tobacco dependence, a chronic disease management strategy that sustains treatment over time is more effective than standard treatment⁵¹ and may be appropriate for smokers having LCS. We will test 3 intervention components—counseling length, medication duration, and systematic screening and referral to community-based services to address social barriers. All treatment will be 1) proactively offered, 2) delivered with MI, 3) personalized to quit motivation and risk perceptions, and 4) coordinated by a central care service.

Challenges to offering cessation services at LCS sites. Integrating cessation services into LCS screening sites (typically high volume practices that lack cessation resources) is a challenge. Most LCS sites report screening patients' smoking status (99%) and advising to quit (91%), but fewer provide cessation counseling or referral (60%); only one-third recommend medications.⁵² Following LCS, primary care clinicians do not often provide any cessation support.⁵³ The deployment of ***health information technology (IT) platforms*** can promote outreach and access at different points in the LCS process, using technologies like patient portals, informational videos, and video-conferencing. In our Project Reach evaluation, patients

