Recruitment Point 3. LDCT Result. After the patient has received the result, patients who have not previously enrolled or refused further contacts will be sent a short video recruitment message tailored to the result via a secure, encrypted email including a secure REDCap survey link, or a letter with a URL to a secure REDCap survey. It will invite them to join the study, and

give brief cessation advice from [name] or [name]. Patients will then be contacted by the RA who will use the same workflow as described for Point 1 (i.e., screen, consent, administer baseline survey). Patients who enrolled at an earlier point will receive a short video embedded in a secure REDCap survey tailored to their test result to address why quitting and study participation remain important.

Hispanic/Latino patients that do not enroll will have MRNs shared with study investigators to be approached for protocol # 2019P002549.

Patients may also be contacted for research purposes from the team in the future.

Recruitment Summary: Our recruitment strategy is designed to require little additional effort at busy radiology sites, but make systematic and repeated recruitment offers to enable us to achieve maximal reach.^{5,50,54,55,56,59} To provide data for our implementation evaluation (Aim 3), we will record the numbers and characteristics of patients who are identified, eligible, and enrolled at each time point. We will document reasons for ineligibility and refusal and document EHR-recorded sociodemographic and biological characteristics, medical history, and cancer history of refusers.

Randomization. Patients will be randomized at the time of enrollment (i.e., completed consent and baseline survey), stratified into 9 randomization strata (3 groups of LCS study sites and 3 recruitment points), to a LCS-tailored intervention treatment arm. The intervention arms will consist of 8 groups of equal proportions, based on a 3-factor fully crossed factorial design to efficiently test components that vary on counseling duration, NRT duration, and provision of systematic referral.

V. STUDY PROCEDURES

Data management. A centralized SQL database will be used for patient identification and recruitment, randomization, patient tracking, and data input. It will interface with all data collection efforts (RAs will enter in REDCap).

Intervention arm components

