This study was initially powered conservatively to detect a smaller risk ratio of 1.4 and did not account for additional power provided through within-person correlation via repeated measurement of our outcome of interest. Initial power calculations, assuming a Type 1 error rate of 0.05, 25% attrition at 6 months, and no within-person correlation showed that our original N of 960 patients (N=480 per condition) gave us 85.0% power to detect a risk ratio of 1.4 with a reference rate of 15%. Updated power calculations accounting for within-person correlation of 0.6 show that this original N gives us 96.8% power to detect our target risk ratio of 1.6, assuming 25% attrition at 6 months and a 15% reference cessation rate.

Our previous power calculation assumed a 25% attrition rate at 6 months. We re-examined this assumption after halfway through the recruitment. Our new estimates are 12.7% attrition rate at 3 months and 15.9% attrition rate at 6 months. Based on these estimates, we further reduce the target recruitment from 720 to 640. Combining data from both 3-month (estimated N=559) and 6-month (estimated N=539) assessments, the effective sample size will be 768 after taking into account of within-person correlation using a conservative estimate of 0.6. The new sample size will have 70% power to detect a risk ratio of 1.6 (10% vs. 16%) and 81% power to detect a risk ratio of 1.7 (10% vs. 17%).

VII.. RISKS AND DISCOMFORTS (Stratify by common and uncommon)

Prior to enrollment, potential patients will be cautioned about the potential negative psychological and physical implications of joining the study and/or quitting smoking.

Psychological Risks

Individuals may find it stressful to answer questions and discuss their smoking behaviors. The risks associated with these discussions are minimal, especially when compared to the benefits of smoking cessation.

The potential risks to subjects include: 1) speaking with a counselor about smoking and/or cancer-related topics has the potential for increasing psychological vulnerability; 2) experiencing physical and emotional withdrawal symptoms from smoking cessation; and 3) potential side effects of using nicotine replacement therapy.

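### The 6-month component comparison is a valid but unadjusted chi-square; fixing the stratification factors and two baseline covariates in one model would probably gain about 1 to 2 points of power (range 0 to about 5)

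*Combined protocol and SAP*

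**What the plan says.** The Outcomes/analysis part of section VI compares each component's two levels on the whole sample. For abstinence at 6 months the method is: "For binary outcomes, chi-square tests will be used to compare the outcomes between groups for each follow-up time". On sites it says: "Data from all PHS sites will be pooled for analysis, after confirming there is no significant heterogeneity among sites or adjusting as needed". No threshold, model or form of adjustment is given.

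Section IV (Randomization) has patients "stratified into 9 randomization strata (3 groups of LCS study sites and 3 recruitment points"). Neither factor is fixed in the component comparison. Recruitment point returns only as point of study entry, in the list of exploratory moderators. Quit motivation and nicotine dependence are in the same list, of which the plan says: "We will test the effects of these factors in multivariable logistic regression models to determine their association with the primary and secondary smoking outcomes". The GEE analysis names no covariates.

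The covariates are collected. The Measures part lists "Current cigarettes/day, number of years smoked, e-cigarette use, past and current use of cessation medication" and the 2-item Heaviness of Smoking Index (HSI), at baseline and follow-up. Readiness to quit is under Proximal Outcomes/Mediators: "All proximal outcomes/mediators will be assessed via survey at baseline and follow-up". The background section says that "heavy smoking, and having strong nicotine dependence are factors associated with less success in quitting".

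**The concern.** Adjusting a randomised comparison for baseline predictors of the outcome, fixed in advance, usually sharpens it without new data. Here the plan stratifies on two factors, measures dependence and readiness before treatment, and itself links heavy smoking and dependence to failure to quit. It then uses none of these as fixed terms in the test of its primary outcome.

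Two things are at stake. One is precision in a comparison with limited power. The other is prespecification: with site adjustment left to a heterogeneity check, the form of the primary analysis depends on the data. Bias and false-positive control are not at stake.

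**Working it through.** **Inputs from the documents.** N = 640, so 320 per level of each component (Factorial design; Outcomes/analysis). Planning rates 10% vs 16% and 10% vs 17%, type I error 0.05, attrition 12.7% at 3 months and 15.9% at 6 months, correlation 0.6 (Sample size/Power calculations; Reduction from initial power calculations). Patients lost to follow-up count as smokers (Analysis plan).

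**Assumed, because the documents are silent.** A two-sided test, and the prognostic strength of strata and covariates.

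**Step 1. Reproduce the plan's figure.** The stated 70% and 81% rest on 3- and 6-month data combined: (559 + 539)/2 × (2 − 0.6) = 768.6, the plan's 768, or 384 per side. Power = Φ{[d − 1.96·√(2p̄(1−p̄)/n)] / √[(p₁(1−p₁) + p₂(1−p₂))/n]}, with d = p₂ − p₁. At n = 384 this gives 69.6% and 81.1%, so the plan's figures reproduce.

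**Step 2. Power of the 6-month chi-square, n = 320 per side.**
- 10% vs 16%: (0.06 − 1.96 × 0.02659)/0.02648 = 0.298, power 61.7%.
- 10% vs 17%: (0.07 − 1.96 × 0.02702)/0.02687 = 0.634, power 73.7%.

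These hold if the planning rates already count missing patients as smokers. If they apply to completers, multiply by 1 − 0.159 = 0.841: 8.41% vs 13.46% gives 53.4%, and 8.41% vs 14.30% gives 65.1%.

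**Step 3. Gain from adjustment, closed form.** If baseline covariates explain a share R² of outcome variance, replace n by n/(1 − R²).

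| R² | 10% vs 16% | 10% vs 17% |
|---|---|---|
| 0 | 61.7% | 73.7% |
| 0.03 | 63.0% (+1.3) | 75.0% (+1.3) |
| 0.05 | 63.9% (+2.2) | 75.9% (+2.2) |
| 0.10 | 66.3% (+4.6) | 78.1% (+4.4) |

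**Step 4. Gain by simulation.** 10,000 trials per scenario, N = 640, permuted blocks of 8 within 3 × 3 strata, one active component, two equally weighted normal covariates, likelihood-ratio test in the logistic model. Entries are power of the chi-square, then of the full adjusted model. Strength is the joint log-odds per SD of the covariates; strata SD is on the logit scale.

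| Strength | 16%, strata SD 0 | 16%, strata SD 0.30 | 17%, strata SD 0 | 17%, strata SD 0.30 |
|---|---|---|---|---|
| 0 | 63.0 → 63.4 | 62.6 → 64.1 | 74.0 → 74.5 | 74.7 → 75.7 |
| 0.3 | 61.8 → 62.8 | 63.0 → 64.8 | 74.8 → 75.8 | 74.2 → 76.0 |
| 0.5 | 61.7 → 63.8 | 62.7 → 65.2 | 74.1 → 75.8 | 75.1 → 76.9 |
| 0.8 | 61.4 → 65.5 | 62.4 → 67.2 | 74.5 → 78.1 | 75.2 → 78.8 |
| 1.0 | 62.1 → 67.3 | 63.0 → 68.5 | 74.5 → 79.7 | 73.8 → 79.5 |

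About 0.5 point of each gain is only the difference between the two tests: it appears when neither strata nor covariates have any effect. Net of that, the gain is about 0 when nothing is prognostic, about 1 to 2 points at strength 0.3 to 0.5, and about 5 at 1.0.

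**Step 5. What those strengths mean.** At a 13% overall quit rate, strength 0.5 corresponds to an AUC of about 0.64 and R² of about 0.03. Strength 1.0 corresponds to an AUC of about 0.75 and R² of about 0.11, with quit rates of about 3% in the lowest quarter of the score and 28% in the highest.

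**Step 6. Type I error (13% vs 13%).** Chi-square 4.9 to 5.0%; adjusted logistic models 5.1 to 5.4%. For the GEE, unadjusted 4.4 to 5.5% and adjusted 4.8 to 5.8%. The GEE covariate step was similar in size (+0.8 and +0.4 at strength 0.3, +5.6 and +5.0 at 1.0), but those runs assumed complete data at both visits.

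**Step 7. Model size.** One intercept, three components, two site-group terms, two recruitment-point terms and two covariates make 10 parameters. Expected quits are 320 × (0.10 + 0.16) = 83.2 to 320 × (0.10 + 0.17) = 86.4, or 70.0 to 72.7 after multiplying by 0.841.

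**The case against.** The strongest reply is that nothing here is wrong. A chi-square on 640 patients randomised in a balanced factorial is a complete, valid analysis, and preferring a regression is a matter of efficiency. That is right, and it limits the point to an optional improvement. A reader might infer that ignoring the strata makes the test invalid or biased. The type I error results do not support that.

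A reader might also take 5 points as the likely gain. The documents do not support that either. The background section calls heavy smoking and strong dependence common among patients eligible for screening, and entry requires at least 20 pack-years, so their spread within the trial may be narrow. Readiness is one item and HSI two. An AUC of 0.75 from these is possible but undocumented.

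A third tempting reading is that missing covariates explain why the 6-month test falls below the stated 70% and 81%, or that adjustment would make good a smaller sample. The stated figures come from combining two visits, which is a separate matter. Even the best simulated case for 10% vs 16% (68.5%) stays under 70%.

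Covariates are not absent from the plan: exploratory logistic models, conditional site adjustment and possible completion weights are there. None of them fixes the component comparison.

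One objection stands in full. The data monitoring plan in section IX foresees interim analyses throughout the trial, with results in annual reports. A change of primary model made after seeing outcomes by component could look data-driven.

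**Conclusion.** The point holds as a low-cost improvement in precision and prespecification. It is not an error. The realistic gain is about 1 to 2 points of power for each component's 6-month comparison, from 0 if the covariates do not predict quitting to about 5 if they are strong. Every non-zero value rests on prognostic strengths that the documents do not give. The starting power is about 62% and 74%, or about 53% and 65% if the planning rates describe completers. The benefit of removing a data-dependent choice about site does not depend on prognostic strength. Confidence is medium: the text is clear, the size is not.

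**What to change.** Make the primary 6-month analysis one prespecified logistic model, locked by people blind to outcomes by component, with the date of locking recorded. Include:
- the three effect-coded components;
- site group and recruitment point as randomised;
- baseline readiness to quit;
- baseline HSI.

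State a simple rule for skipped baseline items, for example single imputation that uses neither treatment nor outcome. Report standardised risk differences and risk ratios for each component, so that the effect stays on the marginal scale. Use the same covariates in the GEE, and keep the chi-square as a sensitivity analysis.

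The cost is protocol wording and a few lines of code on data already collected. The downside is about 10 parameters on about 70 to 86 expected quits, roughly 7 to 9 per parameter, so the covariate list should not grow. If the lock cannot be made blind, keep the chi-square as primary and report the adjusted model as supportive.
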